9.3 Adverse Events and Serious Adverse Events

9.3.1 ***Definition of Adverse Events (AE)***

An adverse event (AE) is any untoward medical occurrence associated with the use of an intervention in humans, whether or not considered intervention related. Intercurrent illnesses or injuries should be regarded as adverse events.

A pre-existing condition should be recorded as an adverse event if the frequency, intensity or the character of the condition changes.

9.3.2 ***Definition of Serious Adverse Events (SAE)***

Adverse events are classified as serious or non-serious. A serious adverse event is any AE that, in the view of either the investigator or the sponsor, is:

- fatal
- life-threatening
- requires or prolongs hospital stay
- results in persistent or significant disability or incapacity
- a congenital anomaly or birth defect
- an important medical event when the event does not fit the other outcomes, but the event may jeopardize the patient and may require medical or surgical intervention (treatment) to prevent one of the other outcomes.

Important medical events are those that may not be immediately life threatening but are clearly of major clinical significance they may jeopardize the participant and may require intervention to prevent one of the other serious outcomes noted above.

9.3.3 ***Classification of an Adverse Event***

9.3.3.1 ***Severity of Event***

For adverse events (AEs), the following guidelines will be used to describe severity.

- Mild – Events require minimal or no treatment and do not interfere with the participant's daily activities.
- Moderate – Events result in a low level of inconvenience or concern with the therapeutic measures. Moderate events may cause some interference with functioning.
- Severe – Events interrupt a participant's usual daily activity and may require systemic drug therapy or other treatment. Severe events are usually potentially life-threatening or incapacitating. Of note, the term "severe" does not necessarily equate to "serious".

9.3.3.2 *Relationship to Study Intervention*

All adverse events (AEs) must have their relationship to the study intervention assessed by the clinician who examines and evaluates the participant based on temporal relationship and his/her clinical judgment. The degree of certainty about causality will be graded using the categories below.

- Related – The AE is known to occur with the study intervention, there is a reasonable possibility that the study intervention caused the AE, or there is a temporal relationship between the study intervention and event. Reasonable possibility means that there is evidence to suggest a causal relationship between the study intervention and the AE.
- Not Related – There is not a reasonable possibility that the administration of the study intervention caused the event, there is no temporal relationship between the study intervention and event onset, or an alternate etiology has been established.

OR

- Definitely Related – There is clear evidence to suggest a causal relationship, and other possible contributing factors can be ruled out. The clinical event, including an abnormal laboratory test result, occurs in a plausible time relationship to study intervention administration and cannot be explained by concurrent disease or other drugs or chemicals. The response to withdrawal of the study intervention (dechallenge) should be clinically plausible. The event must be phenomenologically definitive, with use of a satisfactory rechallenge procedure if necessary.
- Probably Related – There is evidence to suggest a causal relationship, and the influence of other factors is unlikely. The clinical event, including an abnormal laboratory test result, occurs within a reasonable time after administration of the study intervention, is unlikely to be attributed to concurrent disease or other drugs or chemicals, and follows a clinically reasonable response on withdrawal (dechallenge). Rechallenge information is not required to fulfill this definition.
- Possibly Related – There is some evidence to suggest a causal relationship (e.g., the event occurred within a reasonable time after administration of the trial medication). However, other factors may have contributed to the event (e.g., the participant's clinical condition, other concomitant events). Although an AE may rate only as "possibly related" soon after discovery, it can be flagged as requiring more information and later be upgraded to "probably related" or "definitely related", as appropriate.
- Unlikely to be related – A clinical event, including an abnormal laboratory test result, whose temporal relationship to study intervention administration makes a causal relationship improbable (e.g., the event did not occur within a reasonable time after administration of the study intervention) and in which other drugs or chemicals or underlying disease provides plausible explanations (e.g., the participant's clinical condition, other concomitant treatments).
- Unrelated – The AE is completely independent of study intervention administration, and/or evidence exists that the event is definitely related to another etiology. There must be an alternative, definitive etiology documented by the clinician.

9.3.3.3 *Expectedness*

The study team will be responsible for determining whether an adverse event (AE) is expected or unexpected. An AE will be considered unexpected if the nature, severity, or frequency of the event is not consistent with the risk information previously described for the study intervention.

9.3.4 *Time Period and Frequency for Event Assessment and Follow-Up*

Safety will be assessed by monitoring and recording potential adverse effects using the protocol defined grading system at each assessment visit. Participants will be monitored by medical histories. The severity of mild, moderate, severe, life-threatening, and death, corresponding to Grades 1-5, will be used whenever possible.

At each assessment visit (baseline, weeks 12 and 24) study staff will seek information on adverse events by non-directive questioning. Adverse events may also be detected when they are volunteered by the participant during the screening process or between assessment visits. Information on all adverse events will be recorded in the source documentation. To the extent possible, adverse events will be recorded as a diagnosis and symptoms used to make the diagnosis recorded within the diagnosis event.

As much as possible, each adverse event or follow-up information will be evaluated to determine:

1. Severity grade
2. Duration (start and end dates)
3. Relationship to the study treatment or process – [Reasonable possibility that AE is related: No (unrelated/ not suspected) or Yes (a suspected adverse reaction)]. If yes (suspected) - is the event possibly, probably or definitely related to the investigational treatment?
4. Expectedness to study treatment or process
5. Action taken with respect to study or investigational treatment or process (none, treatment adjusted, temporarily interrupted, permanently discontinued, unknown, not applicable)
6. Whether medication or therapy taken (no concomitant medication/non-drug therapy, concomitant medication/non-drug therapy)
7. Whether the event is serious

Once an adverse event is detected, it will be followed until its resolution during the trial or until it is judged to be permanent, and assessment should be made at each visit (or more frequently, if necessary) of any changes in severity, the suspected relationship to the study treatment, the interventions required to treat it, and the outcome.

9.3.5 *Adverse Event Reporting*

Reporting Period

Adverse events will be reported from the time of informed consent until study completion.

Investigator Reporting: Notifying the Study Sponsor

Every SAE, regardless of suspected causality (e.g., relationship to study product(s) or study procedure(s) or disease progression) must be reported to the sponsor within **24 hours** of learning of its occurrence.

Recurrent episodes, complications, or progression of the initial SAE must be reported to the Sponsor as a follow-up to the original episode within 24 hours of the investigator receiving the follow-up information. A SAE considered completely unrelated to a previously reported one should be reported separately as a new event.

New information regarding the SAE will be reported as it becomes available and in the same manner that the initial SAE (i.e. SAE form). The investigator must follow the event to resolution or until the event is deemed and documented irreversible, whichever is longer.

Investigator Reporting: Local Reporting Requirements

The investigator will report AEs and SAEs to the IRB/EC of record and other local regulatory groups per the local requirements.

9.3.6 *Serious Adverse Event Reporting*

The study clinician will immediately report to the sponsor any serious adverse event, whether or not considered study intervention related, including those listed in the protocol and must include an assessment of whether there is a reasonable possibility that the study intervention caused the event. Study endpoints that are serious adverse events (e.g., all-cause mortality) must be reported in accordance with the protocol unless there is evidence suggesting a causal relationship between the study intervention and the event (e.g., death from anaphylaxis). In that case, the investigator must immediately report the event to the sponsor.

New information regarding the SAE will be reported as it becomes available and in the same manner that the initial SAE (i.e. SAE form). All serious adverse events (SAEs) will be followed until satisfactory resolution or until the site investigator deems the event to be chronic or the participant is stable. Other supporting documentation of the event may be requested by the study sponsor and should be provided as soon as possible.

9.4 Unanticipated Problems

9.4.1 *Definition of Unanticipated Problems (UP)*

The Office for Human Research Protections (OHRP) considers unanticipated problems involving risks to participants or others to include, in general, any incident, experience, or outcome that meets all the following criteria:

- Unexpected in terms of nature, severity, or frequency given (a) the research procedures that are described in the protocol-related documents, such as the Institutional Review Board (IRB)-approved research protocol and informed consent document; and (b) the characteristics of the participant population being studied;

- Related or possibly related to participation in the research (“possibly related” means there is a reasonable possibility that the incident, experience, or outcome may have been caused by the procedures involved in the research); and
- Suggests that the research places participants or others at a greater risk of harm (including physical, psychological, economic, or social harm) than was previously known or recognized.

9.4.2 *Unanticipated Problem Reporting*

Unanticipated problems (UPs) such as:

- Complaint of a participant when the complaint indicates unexpected risks, or the complaint cannot be resolved by the research team
- Breach of confidentiality
- Incarceration of a participant when the research was not previously approved under Subpart C and the investigator believes it is in the best interest of the subject to remain on the study
- Premature closure of a study (e.g., due safety, lack of efficacy, feasibility, financial reasons, etc.)

should be reported by the investigator to the National Institutes of Health and reviewing Institutional Review Board (IRB). The UP report will include the following information:

- Protocol identifying information: protocol title and number, PI's name, and the IRB project number;
- A detailed description of the event, incident, experience, or outcome;
- An explanation of the basis for determining that the event, incident, experience, or outcome represents an UP;
- A description of any changes to the protocol or other corrective actions that have been taken or are proposed in response to the UP.

To satisfy the requirement for prompt reporting, UPs will be reported using the following timeline:

- UPs that are serious adverse events (SAEs) will be reported as any other SAE.
- Any other UP will be reported to the Sponsor, IRB and to the DCC/study sponsor within 1 week of the investigator becoming aware of the problem.
- All UPs should be reported to appropriate institutional officials (as required by an institution's written reporting procedures), the supporting agency head (or designee), and the Office for Human Research Protections (OHRP) within 7 days of the IRB's receipt of the report of the problem from the investigator.

10 STATISTICAL CONSIDERATIONS

10.1 Statistical Hypotheses

Primary Efficacy Endpoint(s):

Aim 1: BWL+VOUCHER and BWL+HOME will result in greater weight loss (percent of initial weight) at 24 weeks than BWL-Alone.

Secondary Efficacy Endpoint(s):

Aim 2: BWL+HOME will result in greater weight loss (percent of initial weight) at 24 weeks than BWL+VOUCHER.

Aim 3a: BWL+VOUCHER and BWL+HOME, relative to BWL-Alone, produces greater improvements in health-related quality of life (HRQOL) and dietary quality as assessed by skin carotenoid levels (a fruit and vegetable biomarker) and Healthy Eating Index (HEI) scores from baseline to week 24.

Aim 3b: BWL+HOME, compared to BWL+VOUCHER, produces greater improvements in HRQOL, skin carotenoid levels and HEI scores from baseline to week 24.

10.2 Sample Size Determination

This is an exploratory study. The sample size should be sufficient to provide us with effect size estimates for a larger randomized controlled trial.

10.3 Populations for Analyses

Populations for analyses will include:

- Intention-to-Treat (ITT) Analysis Dataset (i.e., all randomized participants)
- Per-Protocol Analysis Dataset: subset of the participants in the full analysis (ITT) set who complied with the protocol sufficiently to ensure that these data would be likely to represent the effects of study intervention according to the underlying scientific model (e.g., participants attended at least 80% of study intervention visits; participants reported consuming at least 50% of food purchased with food vouchers (BWL+VOUCHER) or 50% of food they received from food boxes (BWL+HOME))

10.4 Statistical Analyses

10.4.1 General Approach

Descriptive statistics and exploratory plots will be generated for all variables of interest. We will conduct initial exploratory data analyses to identify outliers and to assess the distribution of data. Data summaries will be produced both the combined sample, and separately by treatment arm. Continuous variables will be transformed if they are skewed. Categorical variables will be summarized as proportions. Baseline characteristics will be compared among the treatment arms using ANOVAs for continuous variables and chi-square tests for categorical variables. Key baseline variables that differ by treatment arm will be considered for use as covariates in the

analyses described below. Patterns of missing data will be examined. If the missingness mechanism is related to the missing outcome itself, we will use sensitivity analyses to explore how robust our findings are with respect to a range of assumptions regarding missing data.

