10.4.2 Analysis of the Primary Efficacy Endpoint(s)

The two primary outcomes are to test the hypotheses that each of the BWL+VOUCHER and BWL+HOME interventions will result in better weight loss at week 24 compared to BWL-Alone. The primary analysis is an intention-to-treat, between-group comparison of the mean change from baseline (randomization) to week 24 using a linear mixed model. Specifically, we will regress the mean change from baseline on the treatment indicator and baseline weight loss. Significance will be determined using an α cutoff of 0.05. The primary analysis will be an intent-to-treat analysis. The model will include each participant as a random intercept to adjust for within-patient correlation of the repeated measures, fixed predictors of study arm indicators, time indicators, and time by study arm interactions. In addition, sensitivity analyses will be conducted adjusting the model by including baseline variables that either had between-group differences at baseline or that were associated with the likelihood of missing outcomes at a 0.20 significance level.

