10.4.3 Analysis of the Secondary and Exploratory Endpoint(s)

For non-primary comparisons, an α level of 0.05 will be used for significance. We will test the main effects of treatment condition on percent initial weight change at skin carotenoid levels, general health and weight-related quality of life as well as exploratory endpoints using linear mixed models and similar methods as described above. Analyses will use intention-to-treat analyses and will be conducted with and without adjustment for baseline differences in characteristics. We plan to assess for differential effects of the interventions based on sex/gender and race/ethnicity. Separate analyses will be performed for men and women and based on self-identified race/ethnicity, although these will be considered exploratory as there is no strong reason to hypothesize a difference in efficacy based on these characteristics.

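### Covariates for the secondary and sensitivity analyses are picked by testing baseline differences between randomised arms, which recovers almost none of the precision adjustment could give and leaves the lead secondary estimate unnamed

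*Combined protocol and SAP*

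**What the plan says.** Section 10.4.1 sets up the comparison: "Baseline characteristics will be compared among the treatment arms using ANOVAs for continuous variables and chi-square tests for categorical variables". It continues that "Key baseline variables that differ by treatment arm will be considered for use as covariates" in the analyses that follow. It gives no list of key variables, no level at which a variable counts as differing, and no rule for what considering it leads to.

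Section 10.4.2 writes out the primary model: "we will regress the mean change from baseline on the treatment indicator and baseline weight loss", with a random intercept per participant and "fixed predictors of study arm indicators, time indicators, and time by study arm interactions". The data-driven covariates come after that: "In addition, sensitivity analyses will be conducted adjusting the model by including baseline variables that either had between-group differences at baseline". A second criterion for those same sensitivity analyses admits variables related to missingness, screened at 0.20.

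Section 10.4.3 says the secondary and exploratory analyses "will be conducted with and without adjustment for baseline differences in characteristics". It does not say which version is the main result.

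Section 5.5 stratifies randomisation by baseline SNAP/WIC receipt and describes the trial as open-label. The stratification factor is not named in any analysis model.

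**The concern.** The arms are randomised, so the ANOVA and chi-square tests address a null hypothesis known to be true. A small p-value marks a chance imbalance. It does not show that the variable matters for weight change. The gain from adjustment depends on how strongly a covariate predicts the outcome, and the plan never uses that criterion. The rule can therefore admit unrelated variables that happen to be unbalanced and pass over prognostic ones that happen to be balanced.

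Two things are at stake. One is precision: Section 10.2 says the trial exists to supply effect-size estimates for a larger trial, so the width of its intervals is the main product. The other is a single answer per endpoint: two secondary versions of equal standing, one of them with covariates fixed only after the baseline data are seen, leave open which estimate goes forward.

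**Working it through.** The plan states no power, effect size, SD or dropout, so there is no figure of its own to reproduce. The figures below are illustrations.

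**Inputs from the plan.** 105 participants, 1:1:1, so 105/3 = 35 per arm (Synopsis, Section 5.5). Alpha 0.05 (Section 10.4.2); sidedness is not stated and two-sided is assumed.

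**Assumptions not in the plan.** A single week-24 comparison with complete data; a true effect of 0.6 SD, with 0.5 SD as a check; correlation r between one covariate and the outcome of 0.2, 0.3 or 0.5; 5 to 15 independent baseline variables; a variable counted as differing at p<0.05.

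**1. Chance flags.** With k independent variables, P(at least one flagged) = 1 − 0.95^k.
- k = 5: 1 − 0.774 = 23%
- k = 10: 1 − 0.599 = 40%
- k = 15: 1 − 0.463 = 54%

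Any one variable, prognostic or not, has a 5% chance of being flagged.

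**2. What pre-specified adjustment gives.** In SD units, SE = √(1 − r²) × √(2/35), and √(2/35) = 0.239. Power is taken from the noncentral t distribution with 0.6/SE as the noncentrality.

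| r | SE | 0.6/SE | Power at 0.6 SD | Power at 0.5 SD |
|---|---|---|---|---|
| 0 (unadjusted) | 0.239 | 2.51 | 70% | 54% |
| 0.2 | 0.234 | 2.56 | 71–72% | 56% |
| 0.3 | 0.228 | 2.63 | 74% | 58% |
| 0.5 | 0.207 | 2.90 | 82% | 67% |

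The 71–72% depends on whether residual degrees of freedom come from two arms (68) or three (102). As a reduction in SE, 1 − √(1 − r²) is 2%, 5% and 13% for r = 0.2, 0.3 and 0.5.

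**3. What test-then-adjust gives.** Simulation: 8,000 trials per setting, three arms of 35, ten independent baseline variables of which one is prognostic, and adjustment for those with ANOVA p<0.05.
- The prognostic variable was selected in about 5% of trials.
- At 0.6 SD, power was 69–70% with test-then-adjust and 69–70% with no adjustment, at every R² tried (0.1, 0.2, 0.3, 0.5).
- Pre-specifying the prognostic variable gave 74%, 78%, 84% and 94% at those R² values.
- Type I error of the selection rule was 4.2–4.9%. Taking the better of the adjusted and unadjusted p-values gave 5.4–5.6%.

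**The case against.** **The primary analysis is already specified.** A reader might infer that the primary model is to be chosen after results by arm are known. The documents do not support that. Section 10.4.2 writes the model out and puts both screens, for imbalance and for missingness at 0.20, in sensitivity analyses. The trial is open-label, but the documents do not say what the analyst can see when choosing covariates. This objection stands.

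**The sections are compatible.** Section 10.4.1 can be read as the general statement, with 10.4.2 and 10.4.3 saying how it applies. That is a fair reading. What remains is that 10.4.1 is not itself limited to supportive analyses, and 10.4.3 names no lead version.

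**The harm is modest.** A reader might infer inflated type I error; the simulation shows almost none. The gain from adjustment is also small if the covariates are weak: about 2 to 4 percentage points at r = 0.2 to 0.3, and 12 only at r = 0.5. Nothing in the plan shows which applies. The primary model already carries a baseline term, so some of this gain may be in hand there, although a baseline weight loss does not exist at baseline and the term presumably means baseline weight.

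**The chance-flag figures depend on assumptions.** The rule covers only key variables and gives no level for differing. This is why a range of k is shown and the 0.05 is labelled as assumed.

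**The missingness screen is a different tool.** It is not a balance test and affects only a supportive analysis. It is a lesser matter.

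**Conclusion.** The point holds in limited form. Testing for baseline differences is a poor way to choose covariates: in the illustration it performs like no adjustment, and pre-specified adjustment does better at every covariate strength tried. The size runs from 1–2 to 12 percentage points of power at 0.6 SD for r between 0.2 and 0.5, or a 2% to 13% smaller standard error. It rests on the assumed effect, correlations, complete data and a single-timepoint comparison. The practical loss falls mainly on the secondary and exploratory endpoints, where the rule feeds one of two unranked versions, and on the sensitivity analysis. The primary model needs tidying but is not left open, and the validity of the tests is not in question.

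**What to change.** - **10.4.1:** make the baseline table descriptive. Remove the tests and the sentence on variables that differ by arm.
- **10.4.2:** state that the written-out model is the sole primary analysis. Replace the baseline weight loss term with baseline weight. Add the SNAP/WIC stratum and a short list of prognostic covariates fixed now, for example age and sex. In the sensitivity analysis, replace the imbalance criterion with variables named in advance. Doing the same for the 0.20 missingness screen is optional.
- **10.4.3:** use the same covariates plus each endpoint's own baseline value. Name that adjusted version as the lead and the unadjusted one as supportive.

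The cost is wording only, since these variables are already collected at baseline. The downsides are that a chance imbalance in an unlisted variable is not adjusted for in the main model, and that a few degrees of freedom are spent. The change is best made before outcomes by arm are examined.
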